2.2 SAFETY OBJECTIVES

The safety objectives for this study are as follows:

- To evaluate the local and systemic safety and tolerability of intravitreal injections of 10-mg lampalizumab administered Q4W or Q6W relative to sham control
- To evaluate the clinical significance of anti-therapeutic antibodies directed against lampalizumab

2.3 PHARMACOKINETIC OBJECTIVE

The PK objective for this study is to characterize the systemic PK of lampalizumab administered by 10-mg intravitreal injections Q4W or Q6W.

2.4 DIAGNOSTIC OBJECTIVE

A diagnostic objective for this study is to evaluate the prognostic value of the CFI profile biomarker on the mean change in the GA area from baseline as measured by FAF.

2.5 EXPLORATORY OBJECTIVES

The exploratory objectives for this study are as follows:

- To evaluate the effect of lampalizumab compared with sham control, with respect to:
 - Monocular reading speed as assessed by MNRead charts or by Radner Reading Charts
 - Monocular critical print size as assessed by MNRead charts or by Radner Reading Charts
 - Monocular reading acuity as assessed by MNRead charts or by Radner Reading Charts
 - Binocular reading acuity as assessed by MNRead charts or by Radner Reading Charts
- To evaluate the aqueous levels of total lampalizumab and factor D following study treatment
- To evaluate the potential association of genetic variants in CFI and complement-pathway genes with disease characteristics and response to administration of lampalizumab
- To evaluate the relationship of genetic variants in CFI and complement-pathway genes to levels in the blood of messenger RNA (mRNA) and proteins of CFI and complement-pathway genes

[figure not shown]
3. STUDY DESIGN

3.1 DESCRIPTION OF STUDY

This study is a Phase III, double-masked, multicenter, randomized, sham injection-controlled study evaluating the efficacy and safety of a 10-mg dose of lampalizumab administered Q4W or Q6W by intravitreal injections for approximately 96 weeks, excluding screening period, in patients with GA secondary to AMD. The study will randomize approximately 936 patients at approximately 140 investigational sites globally. The site investigators will be qualified ophthalmologists.

The study will consist of a screening period of up to 28 days (–28 to –1) and an approximately 2-year treatment period (Day 1 to Week 92 for the Q4W treatment arms and Day 1 to Week 90 for the Q6W treatment arms; see [Table 2](#) and [Table 3](#), respectively), followed by the final study visit at Week 96. The duration of the study is approximately 2 years (96 weeks) after the last patient is randomized to the study (see [Figure 2](#)).

Figure 2 Study Schema

1 year=Week 48; 1° EP=primary endpoint; 2 year=Week 96; 2° EP=secondary endpoint; CFI Profile BM+=CFI profile biomarker-positive; CFI Profile BM-=CFI profile biomarker-negative; Day -28=end of screening period; Day 1=randomization and first study treatment visit; ITV=intravitreal; Q4W=every 4 weeks; Q6W=every 6 weeks.

Each consented patient must satisfy all eligibility criteria at both the screening period and the Day 1 visit. As part of the screening process, the central reading center will evaluate FAF images, CFPs, and fluorescein angiograms (FA) to provide an objective, masked assessment of patient eligibility. The investigational cobas® CFI profile assay results of blood sample analysis will be used to determine a patient's biomarker-positive or -negative status and must be obtained during the screening period prior to Day 1 visit. Patients must also meet BCVA and other eligibility criteria (see Section 4.1 for details). Screen-failed patients may be eligible for re-screening up to two additional times during the enrollment period of the study. *At re-screening, all screening visit assessments will be performed except for CFI biomarker sample and FA imaging collection, provided that a valid CFI result is available and reading center-eligible FA images were taken within 8 weeks before the new Day 1 visit (randomization).*

Only one eye will be chosen as the study eye. If both eyes are eligible to become the study eye, the eye with the worse visual function as determined by the investigator and the patient will be the study eye. If both eyes have the same visual function, the eye with the larger area of GA will be selected as the study eye.

After screening has been completed, eligible patients will be randomized in a 2:1:2:1 ratio so that approximately 312 patients will receive study drug treatment Q4W and 156 patients will receive sham treatment Q4W for a total of 24 treatments; 312 patients will receive study drug treatment Q6W and 156 patients will receive sham treatment Q6W for a total of 16 treatments. The study population will be enriched (ratio of 1.5:1) for the biomarker-positive population relative to the biomarker-negative population (see Section [3.3.2.2](#)).

Randomization will be stratified by biomarker status (positive vs. negative) (as determined by the investigational cobas[®] CFI Profile assay), baseline BCVA ETDRS chart Snellen equivalent (20/50 or better vs. worse than 20/50), sex (women vs. men), and microperimetry eligibility (yes vs. no).

Patients will be treated according to the dosing schedule for the assigned treatment arms as outlined in [Table 2](#) and [Table 3](#).

Table 2 Every 4 Weeks Dosing Treatment Arms

Treatment Arm	Day Visit		Week Visit																									
	1	8 ^a	4	8	12	16	20	24	28	32	36	40	44	48	52	56	60	64	68	72	76	80	84	88	92	96 ^a		
BM+ Lampalizumab (N = 188)	x		x	x	x	x	x	x	x	x	x	x	x	x	x	x	x	x	x	x	x	x	x	x	x	x		
BM+ Sham (N = 94)	x		x	x	x	x	x	x	x	x	x	x	x	x	x	x	x	x	x	x	x	x	x	x	x	x	x	
BM- Lampalizumab (N = 124)	x		x	x	x	x	x	x	x	x	x	x	x	x	x	x	x	x	x	x	x	x	x	x	x	x		
BM- Sham (N = 62)	x		x	x	x	x	x	x	x	x	x	x	x	x	x	x	x	x	x	x	x	x	x	x	x	x		

^a Study treatment is not administered at the Day 8 visit and Week 96 (final visit).

BM+ = CFI profile biomarker-positive; BM – = CFI profile biomarker-negative.

Table 3 Every 6 Weeks Dosing Treatment Arms

Treatment Arm	Day Visit		Week Visit															
	1	8 ^a	6	12	18	24	30	36	42	48	54	60	66	72	78	84	90	96 ^a
BM+ Lampalizumab (N = 188)	x		x	x	x	x	x	x	x	x	x	x	x	x	x	x	x	
BM+ Sham (N = 94)	x		x	x	x	x	x	x	x	x	x	x	x	x	x	x	x	
BM- Lampalizumab (N = 124)	x		x	x	x	x	x	x	x	x	x	x	x	x	x	x	x	
BM- Sham (N = 62)	x		x	x	x	x	x	x	x	x	x	x	x	x	x	x	x	

^a Study treatment is not administered at the Day 8 visit and Week 96 (final visit).

BM+ =CFI profile biomarker-positive; BM- =CFI profile biomarker-negative

The first study treatment will be administered on the same day as randomization (Day 1 visit). *If a site has an unexpected issue (e.g., the IxRS is not able to assign the study kit), with the Medical Monitor's permission, the patient's first study treatment may be administered within 3 working days of the Day 1 visit. The following assessments will be repeated on the day of the study treatment: slit lamp examination, indirect ophthalmoscopy, and pre- and post-treatment IOP measurement (recorded on Day 1 eCRF and dated accordingly).*

Study treatment visits will be scheduled Q4W (± 5 days) or Q6W (± 5 days) relative to the Day 1 visit date. Randomized patients will have the first intravitreal injection of lampalizumab or sham injection administered by the investigator on Day 1 and will have safety and ocular assessments performed on Day 8 (± 2 days) visit. At the subsequent scheduled visits (Q4W or Q6W), patients will have safety evaluations performed by the investigator prior to receiving study drug or sham injection. They will be contacted by site personnel 4 (± 2) days after each injection to elicit reports of decrease in vision, eye pain, unusual redness, or any other new ocular symptoms in the study eye. If warranted, patients will be asked to return to the clinic as soon as possible for an unscheduled safety assessment visit (see [Appendix 2](#)). Patient self-administered antimicrobials pre- and post-injection may be used at the investigator's discretion. Patients will be instructed to contact the investigator at any time if they have any health-related concerns.

All assessments for a scheduled visit are to be performed on the same day, except those performed during the screening period.

Study treatment should not occur earlier than 22 days after the previous treatment. Missed study treatments will not be made up.

After the Day 1 visit, if a patient misses a study visit when ocular images are scheduled to be taken (see [Appendix 1](#)), the images must be obtained at the next scheduled visit.

Patients are not expected to attend their scheduled visits if there are extenuating circumstances justifying their inability to come to the clinic.

For masking requirements, see [Section 4.2.2](#).

Patients who are prematurely discontinued from study treatment will be encouraged to undergo as many scheduled visits as possible with emphasis on completing Week 48 and Week 96 visits.

Patients discontinued from the study prior to completion will be asked to return for an early termination visit after a minimum of 30 days have elapsed following their last study treatment for monitoring of adverse events and the early termination visit assessments.

3.1.1 Planned Total Sample Size

Approximately 936 patients (188 biomarker-positive patients per treatment group [lampalizumab Q4W, lampalizumab Q6W, and pooled sham] and 124 biomarker-negative patients per treatment group [lampalizumab Q4W, lampalizumab Q6W, and pooled sham]) will be enrolled in the study at approximately 140 sites located globally.

At selected sites, microperimetry assessment will be performed on a subgroup of approximately 138 CFI profile biomarker-positive patients and approximately 90 CFI profile biomarker-negative patients.

At selected sites, serial ECG evaluations will be performed on approximately 100 study patients, independent of CFI profile biomarker status (see Section 4.5.7).

3.1.2 Data Monitoring Committee

An independent Data Monitoring Committee (iDMC) will monitor safety and study conduct on an ongoing basis. Members of the iDMC will be external to the Sponsor and will follow a charter that outlines the iDMC roles and responsibilities. The iDMC will meet approximately every 6 months (frequency adjustable as required) to evaluate the benefit-risk profile of lampalizumab treatment through reviewing both safety *and efficacy* data. No formal efficacy/futility analysis is planned to be done by iDMC. The iDMC may recommend stopping the study early for safety reasons.

A nominal type I error penalty of 0.0001 will be taken for each time the iDMC reviews unmasked data prior to the formal analysis of the primary efficacy endpoint. At the time of the primary efficacy endpoint analysis, it is estimated that five interim data reviews will have been conducted by the iDMC; therefore, efficacy analyses will be performed with a family-wise significance level of 0.0495.

3.2 END OF STUDY

The end of the study is defined as the date when the last patient, last visit (LPLV) occurs. LPLV is expected to occur approximately 96 weeks after the last patient is randomized to the study.

3.3 RATIONALE FOR STUDY DESIGN

3.3.1 Rationale for Lampalizumab Dose and Schedule

To provide assessment of the dose response to lampalizumab and to allow for additional masking for the study, two lampalizumab treatment arms are included in this Phase III study. The 10-mg dose of lampalizumab will be administered intravitreally at Q4W or Q6W intervals.

The 10-mg monthly dosage was the dosing regimen that was found to be the most efficacious and was also well tolerated in the Phase II component of Study CFD4870g.

Lampalizumab—F. Hoffmann-La Roche Ltd
43/Protocol GX29176, Version 6

In Study CFD4870g, the 10-mg every-other-month dosing regimen did not result in efficacy for the overall study population but did result in efficacy in the biomarker-positive group. On the basis of PK/pharmacodynamic (PD) and efficacy modeling of the biomarker-positive group, 10 mg administered Q6W is expected to achieve lower but efficacious drug exposures relative to 10-mg Q4W. Additionally, the Q6W dosing regimen represents less of a treatment burden to patients, caregivers, and physicians relative to a Q4W dosing regimen.

Taken together, the two dosing regimens included in this Phase III study are expected to demonstrate a dose response, with 10-mg Q4W expected to provide maximally feasible efficacious dosage, whereas the 10-mg Q6W is expected to be an effective dose while reducing treatment burden to patients, caregivers, and physicians.

3.3.2 Rationale for Patient Population and Analysis Groups

3.3.2.1 Rationale for Evaluating Lampalizumab Treatment Effect in Patients with Geographic Atrophy Secondary to Age-Related Macular Degeneration

Currently, there are no approved treatments to prevent the progression of GA secondary to AMD and the associated decrease in visual function. Consequently, a significant unmet need exists for treatment of this serious condition. This study will enroll a target population of patients with the diagnosis of GA secondary to AMD. Key eligibility criteria were chosen to enrich the study population for GA patients who may have more rapid growth of GA lesions to maximize the chances of detecting progression of disease and treatment effects over the planned study duration as well as to identify the patients most likely to potentially benefit from the treatment. The key eligibility criteria and rationale for the criteria are presented below:

Evidence of Geographic Atrophy in Both Study Eye and Non-study (Fellow) Eye

Bilateral GA represents the majority of the population (approximately 60%–67%) diagnosed with GA as reported in two natural history studies ([Holz et al. 2007](#); [Sunness et al. 2007](#)) and has been associated with an increased rate of GA lesion growth compared to unilateral GA ([Sunness et al. 2007](#)).

Presence of Hyperautofluorescence Adjacent to the Geographic Atrophy Area in the Study Eye (i.e., Banded or Diffuse Junctional Fundus Autofluorescence Patterns)

Holz et al. ([2007](#)) described four major perilesional FAF patterns (none, focal, banded, and diffuse) that were correlated with the rate of GA lesion growth in the longitudinal natural history arm of patients with GA secondary to AMD in the multi-center FAM-study. Holz reported that GA lesions with banded or diffuse junctional patterns expanded at a significantly higher rate than lesions with focal or no hyperautofluorescence. Of note, approximately 70% of the patients in the FAM study exhibited the banded or diffuse junctional perilesional FAF patterns.

Lampalizumab—F. Hoffmann-La Roche Ltd
44/Protocol GX29176, Version 6

Best Corrected Visual Acuity 20/100 or Better (Snellen Equivalent) in the Study Eye Using Early Treatment Diabetic Retinopathy Study Chart

Sunness et al. (1999b) have reported on populations of patients with GA who may have worsening of VA loss in a manner and timeframe that would be suitable for study in a clinical study. In a study of the natural history of GA, approximately 41% of patients with GA with baseline VA of 20/50 or better lost at least three lines of vision at 2 years and 70% by 4 years. Among these, patients with VA 20/100 or better but worse than 20/50, 15% lost at least three lines of vision at 2 years.

Association between Female Sex and Rate of GA Progression

Caire et al. reported on a prospective study of 73 patients with GA in which they evaluated whether certain genetic and demographic risk factors were associated with the progression of established GA secondary to AMD. In the logistic regression analysis, Caire et al. reported a statistically significant risk association between female sex and the rate of progression of GA ($p=0.02$ with an adjusted odds ratio of 7.31 [95% CI of 1.30-41.80]; Caire et al. 2014).

A similar trend of females having a faster rate of GA progression relative to males was also observed in the Phase II Study CFD4870g. At month 18, the subgroups of female vs. male patients had a mean change from baseline in GA area of 3.831 mm² with 80% CI of (3.340, 4.321) and 2.310 mm² with 80% CI of (1.813, 2.808). Similar trends were also noted when evaluating the subgroups of sex by CFI profile biomarker status. Note that the subgroups analyses in the Phase II study contained small numbers and should be interpreted with caution.

3.3.2.2 Enrichment of Complement Factor I Profile Biomarker-Positive Patients

Exploratory analyses of the Phase II component of Study CFD4870g suggest that the CFI profile biomarker-positive population may have a greater benefit from lampalizumab treatment than the CFI profile biomarker-negative population. As the data from this Phase II study were exploratory and hypothesis-generating (based on a small sample size), the Phase III study population will be enriched (ratio of 1.5:1) for the CFI profile biomarker-positive population relative to the CFI profile biomarker-negative population. Enriching for CFI profile biomarker-positive patients ensures a comprehensive evaluation of the CFI profile biomarker-positive population while, importantly, also studying a sufficient number of the CFI profile biomarker-negative patients to allow adequate benefit-risk assessment in this group. Biomarker status will be determined using the investigational cobas[®] CFI profile assay that will be run at a designated study laboratory testing site.

The cobas[®] CFI Profile Clinical Trial Assay

A valid CFI biomarker result will be determined at a designated study laboratory testing site using the cobas[®] CFI Profile Clinical Trial Assay (CTA), which is a real-time polymerase chain reaction (PCR) test developed by Roche Molecular Systems to

identify genotypes of three SNPs associated with CFH, CFI, and C2/CFB in DNA extracted from whole blood samples from patients with GA secondary to AMD. The cobas[®] CFI Profile CTA is intended to be used as an Investigational Use Only assay to characterize the complement factor profile of study participants. The cobas[®] CFI Profile CTA biomarker status results will then be used to stratify patients at randomization.

The cobas[®] CFI Profile CTA consists of two kits and will use the cobas[®] 4800 platform. The cobas[®] DNA Sample Preparation Kit (DNA isolation kit) provides the necessary components to manually extract genomic DNA from whole blood samples. The cobas[®] CFI Profile CTA contains the necessary PCR master mix, oligonucleotides, cofactor, and controls to detect three SNPs associated with CFI, CFH, and C2/CFB.

3.3.3 Rationale for Control Group

A sham control group will be used in this study to assess the differences in GA progression, change in clinical function measures, and safety in patients who receive lampalizumab compared with patients who receive sham. Patients randomized to the sham control group will undergo the same assessments as patients randomized to the study drug intravitreal injection group.

Sham injections were chosen instead of placebo intravitreal injections to minimize the known risk of intravitreal injection-related adverse events (e.g., endophthalmitis) and because no potential patient value would be derived from an intravitreal injection of placebo.

3.3.4 Rationale for Biomarker Assessments

The response to lampalizumab treatment will be evaluated in pre-specified subgroups defined by the genetic biomarker test (cobas[®] CFI Profile Trial Assay) based on the common genetic variants of CFI, CFH, and C2/CFB. The whole blood sample CFI profile results will be determined by utilizing an investigational cobas[®] CFI Profile CTA (see [Appendix 22](#)) at the designated central laboratory. Although the CFI profile test is based on the common genetic variants of CFI, CFH, and C2/CFB test, recent studies have identified rare variants in CFI that have been associated with increased AMD risk ([van de Ven et al. 2013](#)). Given the potential for rare variants in CFI and other complement pathway genes to affect disease characteristics including progression and the response to lampalizumab treatment, additional exploratory genetic analysis will be conducted using the biomarker clinical genotyping sample including sequencing of CFI and other complement-pathway genes.

In addition to the genetic analysis, pre-injection plasma levels and whole blood mRNA levels of CFI and complement-pathway genes will be measured. Exploratory analyses will evaluate the relationship of blood levels of CFI and complement-pathway mRNA and proteins to genetic variants in the complement pathway and to disease characteristics, including progression and the response to lampalizumab treatment.

3.4 OUTCOME MEASURES

3.4.1 Efficacy Outcome Measures

The primary efficacy outcome measure for this study is GA area at 1 year as assessed by FAF.

The secondary efficacy outcome measures for this study over time are as follows:

- Number of scotomatous points assessed by mesopic microperimetry for the evaluation of the macular functional response
- Change in macular sensitivity as assessed by mesopic microperimetry for the evaluation of the macular functional response
- GA area as assessed by FAF
- BCVA score as assessed by ETDRS chart at a starting distance of 4 m
- BCVA score as assessed by ETDRS chart under low luminance conditions at a starting distance of 4 m
- Binocular reading speed as assessed by MNRead charts or Radner Reading Charts
- Binocular critical print size as assessed by MNRead charts or Radner Reading Charts
- NEI VFQ-25 composite score
- NEI VFQ-25 near activity subscale score
- NEI VFQ-25 distance activity subscale score
- FRI Index score

3.4.2 Safety Outcome Measures

The safety outcome measures for this study are as follows:

- The incidence and severity of ocular adverse events
- The incidence and severity of systemic (non-ocular) adverse events
- Changes and abnormalities in ECG parameters
- The incidence of anti-lampalizumab antibodies

3.4.3 Pharmacokinetic Outcome Measure

The PK outcome measure for this study is serum lampalizumab concentration over time.

3.4.4 Diagnostic Outcome Measure

The evaluation of the prognostic value of the CFI profile biomarker will be based on the biomarker status at baseline and the primary clinical outcome of change in the GA area from baseline as measured by FAF.

3.4.5 Exploratory Outcome Measures

The exploratory outcome measures for this study are as follows:

- Monocular reading speed as assessed by MNRead charts or Radner Reading Charts over time
- Monocular critical print size as assessed by MNRead charts or Radner Reading Charts over time
- Monocular reading acuity as assessed by MNRead charts or Radner Reading Charts over time
- Binocular reading acuity as assessed by MNRead charts or Radner Reading Charts over time
- Total lampalizumab and factor D levels in aqueous humor as assessed by ELISA
- The association of genetic variants in CFI and complement-pathway genes with disease characteristics and response to administration of lampalizumab
- The relationship of genetic variants in CFI and complement-pathway genes to levels in the blood of mRNA and proteins of CFI and complement-pathway genes

3.5 EXPLORATORY SUBSTUDIES

At selected sites, the Sponsor may propose exploratory substudies associated with the Study GX29176 protocol. Each substudy will be documented in a separate substudy protocol and associated ICF(s).

4. MATERIALS AND METHODS

4.1 PATIENTS

Patient Selection and Sex Distribution

Written informed consent will be obtained prior to initiation of any study procedures. The screening evaluation will be performed within 28 days preceding the Day 1 visit (the day of the first study treatment).

Note: Some patients may require an extended screening period as a result of repeated evaluation of images or other issues. Upon agreement with the Medical Monitor, the screening period may be extended for up to 5 days for such cases.

Only one eye will be chosen as the study eye. If both eyes are eligible, the eye with the worse visual function (as determined by the investigator and patient) will be the study eye. If both eyes have the same visual function, the eye with the larger area of GA will be selected as the study eye.

The protocol allows enrollment of both men and women, provided the entry criteria are met. However, women who are pregnant or breastfeeding will be excluded from the study. The remaining inclusion/exclusion criteria apply to both male and female patients and pertain to issues of patient health performance and safety.

4.1.1 **Inclusion Criteria**

Patients must meet the following criteria for study entry:

General Inclusion Criteria

- Willingness and the ability to provide signed informed consent. Additionally, at U.S. sites, patients must provide Health Insurance Portability and Accountability Act (HIPAA) authorization, and in other countries, as applicable according to national laws.
- Age ≥ 50 years
- For women of *childbearing potential*: agreement to remain abstinent (*refrain from heterosexual intercourse*) or use contraceptive methods that result in a failure rate of $< 1\%$ per year during the treatment period and for at least 30 days after the last dose of study drug

A woman is considered to be of childbearing potential if she is postmenarcheal, has not reached a postmenopausal state (≥ 12 months of amenorrhea with no identified cause other than menopause), and has not undergone surgical sterilization (removal of ovaries and/or uterus).

Examples of contraceptive methods with a failure rate of $< 1\%$ per year include bilateral tubal ligation, male sterilization, established, proper use of hormonal contraceptives that inhibit ovulation, hormone-releasing intrauterine devices and copper intrauterine devices.

The reliability of sexual abstinence should be evaluated in relation to the duration of the clinical trial and the preferred and usual lifestyle of the patient. Periodic abstinence (e.g., calendar, ovulation, symptothermal, or postovulation methods) and withdrawal are not acceptable methods of contraception.

For men: Agreement to remain abstinent or use contraceptive measures and agreement to refrain from donating sperm, as defined below:

With female partners of childbearing potential, men must remain abstinent or use a condom plus an additional contraceptive method that together result in a failure rate of $< 1\%$ per year during the treatment period and for at least 30 days plus 90 days (a spermatogenesis cycle) after the last dose of study drug. Men must refrain from donating sperm during this same time period.

- Ability and willingness to undertake all scheduled visits and assessments
- Valid CFI profile biomarker result (i.e., CFI profile biomarker-positive or CFI profile biomarker-negative)

Ocular Inclusion Criteria: Study Eye

- BCVA letter score of ≥ 49 letters (Snellen equivalent of 20/100 or better) using ETDRS charts at starting distance of 4 m

If BCVA letter score is ≥ 79 letters (Snellen equivalent of 20/25 or better), at least one GA lesion must be within 250 μm of the foveal center

- Well demarcated area(s) of GA secondary to AMD with no evidence of prior or active CNV

The total GA lesion size $\geq 2.54 \text{ mm}^2$ (approximately ≥ 1 disc area [DA]) and $\leq 17.78 \text{ mm}^2$ (approximately ≤ 7 DA) and must reside completely within the FAF imaging field (Field 2–30 degree image centered on the fovea)

If GA is multifocal, at least 1 focal lesion must be $\geq 1.27 \text{ mm}^2$ (approximately ≥ 0.5 DA)

- Presence of hyperautofluorescence of either banded or diffuse patterns adjacent to the area of GA
- Sufficiently clear ocular media, adequate pupillary dilation, and fixation to permit quality fundus imaging

Ocular Inclusion Criteria: Non-study Eye

GA secondary to AMD with no evidence of prior or active CNV

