5.4.3 Reporting Requirements for Pregnancies

5.4.3.1 Pregnancies in Female Patients

Female patients of childbearing potential will be instructed to immediately inform the investigator if they become pregnant during the study or until the last study visit. A *Clinical Trial Pregnancy Reporting Form* should be completed and *submitted to the Sponsor or its designee* immediately (i.e., no more than 24 hours after learning of the pregnancy), *either by faxing or by scanning and emailing the form using the fax number or email address* provided to investigators. Pregnancy should not be recorded on the

Adverse Event eCRF. The investigator should discontinue study drug and counsel the patient, discussing the risks of the pregnancy and the possible effects on the fetus. Monitoring of the patient should continue until conclusion of the pregnancy. Any SAEs associated with the pregnancy (e.g., an event in the fetus, an event in the mother during or after the pregnancy, or a congenital anomaly/birth defect in the child) should be reported on the Adverse Event eCRF. *In addition, the investigator will submit a Clinical Trial Pregnancy Reporting Form when updated information on the course and outcome of the pregnancy becomes available.*

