5.4.3.2 Pregnancies in Female Partners of Male Patients

Male patients will be instructed through the Informed Consent Form to immediately inform the investigator if their partner becomes pregnant during the study or until the last study visit. *A Clinical Trial Pregnancy Form should be completed and submitted to the Sponsor or its designee immediately (i.e., no more than 24 hours after learning of the pregnancy) either by faxing or by scanning and emailing the form using the fax number or email address provided to investigators. Attempts should be made to collect and report details of the course and outcome of any pregnancy in the partner of a male patient exposed to study drug. The pregnant partner will need to sign an Authorization for Use and Disclosure of Pregnancy Health Information to allow for follow-up on her pregnancy. After the authorization has been signed, the investigator will submit a Clinical Trial Pregnancy Reporting Form when updated information on the course and outcome of the pregnancy becomes available. An investigator who is contacted by the male patient or his pregnant partner may provide information on the risks of the pregnancy and the possible effects on the fetus, to support an informed decision in cooperation with the treating physician and/or obstetrician.*

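### Male patients must use contraception for 120 days after the last dose, but are asked to notify a partner's pregnancy only up to the last study visit, 28 or 42 days after that dose for completers

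*Protocol*

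**What the plan says.** Protocol Section 4.1.1 sets two contraception periods. Women of childbearing potential must abstain or use effective contraception "during the treatment period and for at least 30 days after the last dose of study drug". Men with partners of childbearing potential must do so, and must not donate sperm, during treatment and "for at least 30 days plus 90 days (a spermatogenesis cycle) after the last dose of study drug".

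The notification instructions end at a different point. Section 5.4.3.2 has male patients told, through the consent form, to "immediately inform the investigator if their partner becomes pregnant during the study or until the last study visit". Section 5.4.3.1 has female patients told to "immediately inform the investigator if they become pregnant during the study or until the last study visit".

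Section 3.1 fixes the dates. Treatment runs "Day 1 to Week 92 for the Q4W treatment arms and Day 1 to Week 90 for the Q6W treatment arms", "followed by the final study visit at Week 96". Tables 2 and 3 of that section state that no treatment is given at Week 96. Patients who leave the study early are asked back for a termination visit at least 30 days after their last treatment (Sections 3.1 and 4.6).

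Three other sections bear on what happens later:

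- Section 5.4 lists pregnancies among the events an investigator must report within 24 hours of learning of them, and gives no end date.
- Section 5.5.1 follows to outcome those pregnancies that were reported during the study.
- Section 5.6 asks for serious adverse events after the last visit, if the investigator becomes aware of them and they are believed related to study drug. Sections 5.4.3.3 and 5.4.3.4 class abortions and birth defects as serious.

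**The concern.** The protocol gives a reason for the longer period in men: it adds one spermatogenesis cycle to the 30 days. It therefore treats conception during those 120 days as something to guard against. It also has a full system for pregnancies: a 24-hour report, partner authorization, and follow-up to outcome. That system depends on the patient telling the site, and the instruction to do so lapses at the last visit, when most of the men's period is still to run.

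What is at stake is information on the outcome of partner pregnancies conceived inside the period the protocol itself sets. If nobody prompts the man to call, the site may never hear of the pregnancy, and the outcome is hard to recover later. No efficacy conclusion is affected.

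**Working it through.** **Check of the last-dose dates.** The protocol's treatment counts can be reproduced from the visit tables in Section 3.1.

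- Q4W: Day 1 plus Weeks 4 to 92 in steps of 4 = 1 + 23 = 24 treatments. The protocol says "156 patients will receive sham treatment Q4W for a total of 24 treatments", so the last dose is at Week 92.
- Q6W: Day 1 plus Weeks 6 to 90 in steps of 6 = 1 + 15 = 16 treatments, which is the protocol's figure. The last dose is at Week 90.

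**Days from last dose to last visit, for patients treated to the end.** Formula: (96 − week of last dose) × 7.

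- Q4W: (96 − 92) × 7 = 28 days
- Q6W: (96 − 90) × 7 = 42 days

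Each visit may fall 5 days either side of its target. A late dose with an early final visit shortens the interval by 10 days, and the reverse lengthens it by 10. The ranges are 18 to 38 days (Q4W) and 32 to 52 days (Q6W).

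**Days outside the notification instruction.** Formula: max(0, contraception period − days to last visit). The period is 30 + 90 = 120 days for men and 30 days for women.

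| Group | Days to last visit | Days outside | Share of period |
|---|---|---|---|
| Men, Q4W, nominal | 28 | 120 − 28 = 92 | 77% |
| Men, Q4W, with windows | 18 to 38 | 102 to 82 | 85% to 68% |
| Men, Q6W, nominal | 42 | 120 − 42 = 78 | 65% |
| Men, Q6W, with windows | 32 to 52 | 88 to 68 | 73% to 57% |
| Men, early termination at day 30 | 30 | 120 − 30 = 90 | 75% |
| Women, Q4W, nominal | 28 | 30 − 28 = 2 | 7% |
| Women, Q4W, with windows | 18 to 38 | 12 to 0 | 40% to 0% |
| Women, Q6W, nominal and with windows | 42 (32 to 52) | 0 | 0% |
| Women, early termination at day 30 or later | 30 or more | 0 | 0% |

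For men, no combination of windows closes the gap for those treated to the end of the schedule. A man who stops treatment but stays in follow-up has a longer interval, and the gap disappears once his last dose is 120 days or more before his last visit.

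**Whether another section closes it.** Section 5.5.1 does not, because it starts from pregnancies already reported during the study. Section 5.6 does so only in part. It can reach an abortion or a birth defect, but only one believed related and only if the site happens to hear of it. Section 5.4 covers any pregnancy that the investigator learns of, but it gives the patient no reason to call.

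**The case against.** The strongest reply is that nothing here contradicts anything else. A contraception period is a precaution and a notification period is a reporting rule; the first can be longer than the second, and both can be followed as written. That stands, and the point is one of alignment. It does not remove the practical effect: following the notification rule as written stops the prompt inside the period the protocol chose.

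Three stronger readings are tempting and are not supported.

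- A reader might infer that women are left uncovered for most of their period. They are not: Q6W women and early terminators have no gap, and the Q4W shortfall is nominally 2 of 30 days. The 12-day figure needs a dose at the late edge of its window and a final visit at the early edge.
- A reader might infer that later pregnancies would go unreported. The last-visit limit attaches to what patients are told to notify. Section 5.4 has no such limit for a pregnancy the investigator learns of, and Section 5.6 can reach related abortions and birth defects.
- A reader might infer that safety comparisons between arms are biased, because 92 days differ from 78. Each regimen has its own sham arm on the same visit schedule. Pregnancy is not a listed safety outcome (Protocol 3.4.2, SAP 2.1.6), and SAP Section 4.7 plans no summary of it.

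It is also fair to say that events will be rare. Patients are at least 50 years old, systemic drug levels are expected to be low (Section 5.1), and one third of patients receive sham. The age limit does not, however, apply to the partners of male patients.

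**Conclusion.** The point holds for partners of male patients. For men treated to the end of the schedule, 92 of 120 days (77%, Q4W) or 78 of 120 days (65%, Q6W) of the contraception period fall after the notification instruction has ended. With the visit windows the range is 57% to 85%, and 90 days remain if early termination is at day 30. For women there is only the nominal 2-day shortfall in Q4W.

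This rests on the last doses being given at Weeks 92 and 90 and the final visit at Week 96. The counts treat a pregnancy as notifiable from the day of conception. Any delay before it is recognized would lengthen the uncovered stretch, but the documents give no figure for that and the conclusion does not need one. The documents give no expected pregnancy rate; few events are likely. The consent form, through which men receive the instruction, was not available for review and may already say something different.

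**What to change.** Reconcile the notification period in Section 5.4.3.2 with the after-last-dose period in Section 4.1.1. Do the same in Section 5.4.3.1 for the nominal Q4W shortfall in women. Notification should run to the later of the last study visit and the end of the contraception period stated in 4.1.1. Extend Section 5.5.1 so that pregnancies notified in that added time are also followed to outcome. Check that the consent form carries the same instruction, and amend it if it does not.

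The change is to protocol wording and possibly consent wording. It adds no visit or test, and leaves the dosing schedule and the contraception requirements as they are. The downside is a small reporting burden on sites after Week 96: up to 92 days (Q4W) or 78 days (Q6W) on the nominal schedule for male patients, during which a call may come in, and then follow-up of any pregnancy reported.
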